#### 5.6 Source data

Source data will include all questionnaires completed by the patient during their involvement in the study. The patient's medical notes will be considered as the source for data collected on paper CRFs (most baseline and post-operative data during the index admission, and 6 weeks, 6 months and subsequent 6 monthly contacts with a SCN). The source for surgical details will be the data entered into the e-CRF (these are not routinely collected in medical records or operation notes).

Results of any scans, particularly CT, will be considered as source data for those patients that undergoing imaging to assess PSH. Finally, additional HES data will be extracted, which will be considered as source data.

#### 5.7 Selection of confounders

The challenges of confounding have been described above (see 0). We will be able to inspect the accruing data to find out how participating surgeons choose particular surgical variants in relation to participants' characteristics. Assuming that analyses will need to take confounding into account by one method or another, we will consider the list of confounding factors in **Table 5**.

#### Table 5: List of confounding factors

1.	Baseline Clinical Details
	- Age
	- Anthropometry: body mass index
2.	Medical History / Current Health Status:
	- Diabetes
	- Chronic kidney disease
	- Previous abdominal surgery
	- Abdominal wall hernia
	
 
Muscular or connective tissue disorder (e.g. aneurysm disease, Ehlers-danlos syndrome, Marfan syndrome, ostergenesis imperfecta, scleroderma, rheumatoid arthritis, SLE)
 

	- Parity (for females)
	- Frailty score
3.	Current Health Status
	- Smoking history (non-smoker, ex-smoker (minimum 3 months tobacco free), current smoker)
	- Corticosteroid use within 6 months of index surgery
4.	Neoadjuvant treatment
	
 
Treatments in the last 6 months relating to the primary reason for stoma formation (e.g. diseases resection / debulking, chemoradiotheraphy, chemotherapy or radiotherapy)
 

5.	Indication for Surgery
	- Inflammatory Bowel Disease
	- Diverticular Disease
	- Functional Intestinal disorder
	- Tumour (benign or malignant)
6.	Lifestyle and Behaviour
	- Abdominal exercise
	- Use of support garments

Baseline confounding factors will be collected during the admission for the index surgery. One additional item collected will be information about a participant's use of abdominal exercises aimed at improving core muscles and support garments, which will be documented at 6 weeks, 6 months and 12 months by SCNs when participants have started to become used to having a stoma. Although this item relates to a period of time after the index surgery, it is not expected to be influenced by the surgical methods used, not least since participants and SCNs will not know what methods were used.

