## 2. Background

## 2.1 The clinical problem

The prevalence of all types of abdominal stomata in the UK is about 100,000 and 20,000 new stomata are created annually [1]. However, the incidence of PSH is more difficult to assess due to a lack of prospective data and heterogeneity in how clinical and symptomatic PSH are defined. In the current literature, rates of PSH of up to 40% have been reported, varying according to follow-up duration, stoma type and diagnosis method.

To date a variety of methods have been used to diagnose PSH both clinically and symptomatically. Clinically, PSH has been diagnosed from intra-operative findings, clinical examination and computerised tomography (CT). Clinical examination has poor inter-observer reliability [2] and the European Hernia Society (EHS) considers CT to be best way to detect PSH when following up patients with stomata [3]. However, an 'anatomical' PSH detected by CT may not cause symptoms. Symptomatic PSH have typically been identified from health-related quality of life (HRQoL) assessments but the appropriateness of using particular HRQoL tools to detect problems specific to PSH is uncertain. Regardless of the method of clinical or symptomatic diagnosis, PSH can have substantial physical, psychological and economic consequences.

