## 2.2.2 The economic burden of PSH

The economic impact of PSH on the NHS is poorly understood because accurate data regarding stomata are difficult and expensive to extract [7]. However, it has been reported that patients with symptomatic stoma are more likely to have increased rates of consultation with community healthcare teams [8], and increased direct costs related to stoma bags and associated products such as belts, adhesives, sprays, wipes and barrier creams. The cost of stoma bags and associated products was over £228m in 2012 in England alone [9] and costs have risen over 30% in the past 5 years. Skin irritation, one of the commonest problems associated with PSH, is estimated to cost an additional 50 Euro per patient over a 7 week treatment period [10]. The cost of bags and accessories for a patient managing a stoma effectively varies between £780 and £1800 per year; this sum can rise to £6000 per year when a PSH is present [11]. Furthermore, none of the estimated costs incorporate the expense and / or time of the approximately 600 stoma care nurses (SCNs) in the UK.

Some PSH may be repaired surgically and emergency surgical intervention is indicated in some circumstances, e.g. if a PSH causes bowel obstruction. The precise number of PSH repair procedures performed annually in the NHS is currently unknown due to variation in coding. PSH repair performed as elective surgery may be recorded alone or as part of a more complex incisional hernia repair; emergency repair may be recorded as part of a laparotomy. Regardless of coding, PSH repair is associated with significant costs including: the patient's in-hospital stay (including in critical care units), theatre time, intra-operative equipment used and the cost of mesh implants. Unfortunately, complications following PSH repair surgery are common and the hernia recurrence rate is high, leading to further interventions [12-14].

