#### 4.6 Primary and secondary outcomes

#### 4.6.1 Primary outcome

The primary outcome will be PSH incidence during follow-up after index surgery to form a stoma. An incident PSH is defined as:

- Symptoms of PSH (see 5.4), and
- Anatomical PSH, ascertained by independent reading of a CT scan (6)

Participants will describe their PSH symptoms using a custom-designed questionnaire, the "stoma questionnaire" [34]. Symptoms will be classified as green (asymptomatic), amber (mild/moderate symptoms) or red (severe symptoms). Cut-off points for these classifications will be defined on the basis of on-going data collection. We anticipate that severe symptoms may include recurrent problems with the stoma appliance, pain, or admission to hospital with obstruction. Mild/moderate symptoms are likely to be associated with discomfort and ill-fitting appliance issues managed by the patients themselves.

CT scans carried out in the course of a patient's usual NHS care will be assessed for all participants, with anatomical PSH being graded using the EHS classification (EHS class I, II, III or IV [24]). CT scans taken up to 6 months before or 3 months after the stoma questionnaire is completed will be valid for assessing anatomical PSH. The combination of symptomatic PSH and anatomical PSH confirmed by CT imaging will be our primary outcome. CT assessors will collect additional details from CTs (e.g. linear measurement of the PSH defect rather than just defect size >5cm vs ≤5cm), including a measure of the size of the PSH. The ESH criteria for classifying PSH as small or large will be reviewed on the basis of these additional data as the study progresses.

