#### 8. Statistical analyses

#### 8.1 Plan of analysis

The data will be analysed according to the intention to implement a surgical step and will be reported in accordance with the principles of the CONSORT guidelines (but not items relating to randomization). A detailed statistical analysis plan will be prepared prior to locking the database. The primary outcome, time to PSH (defined as the time when PSH confirmed by imaging) and secondary time-to-event outcomes, will be analysed using survival methods. The models will take account of the hierarchical structure of the data; i.e. participants, nested within surgeons nested within centres. The hazards of key predictors will be estimated, with 95% confidence intervals, after adjusting for important procedure, patient and surgeon confounding factors.

Exploratory analyses will be used to inform the choice of survival distribution (e.g. Weibull). The factors included in the model, the modelling strategy and the approach to handling correlated covariates will be documented in the statistical analysis plan. Participants free from a PSH at final follow-up will be censored. Follow-up will also be censored if bowel continuity is restored, if participants have a redo stoma or die. These circumstances leading to censoring may be informative and sensitivity analyses (setting survival times to the longest observed times) will be undertaken to assess the potential impact of informative censoring. Secondary continuous outcomes will be analysed using a mixed regression models, again taking account of the hierarchical structure of the data and the repeated measurements over time. Binary outcomes (e.g. complications) will be analysed using

logistic regression. If the frequency of the outcomes allows, these models will also take account of the hierarchical structure of the data.

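### Table 5 lists exercise and support-garment use, recorded up to 12 months after surgery, as confounders of technique on a justification that overlooks the hernia's own effect on them

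*Protocol*

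**What the plan says.** Section 5.7 says of the coming analyses that "we will consider the list of confounding factors in" Table 5. The last group in that table, Lifestyle and Behaviour, contains abdominal exercise and use of support garments. The text below the table says this information is collected after surgery, "which will be documented at 6 weeks, 6 months and 12 months by SCNs". It gives one reason for treating it like a baseline factor: "it is not expected to be influenced by the surgical methods used, not least since participants and SCNs will not know what methods were used".

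Section 8.1 defines the primary outcome as "time to PSH (defined as the time when PSH confirmed by imaging"), and says hazards will be estimated "after adjusting for important procedure, patient and surgeon confounding factors". It leaves the factors in the model and the modelling strategy to the SAP.

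On timing, section 4.6.1 says "CT scans taken up to 6 months before or 3 months after the stoma questionnaire is completed will be valid for assessing anatomical PSH". Section 5.4 relies on usual-care scans and aims to review at least one in each year of follow-up.

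Section 2.2.2 reports that patients with a symptomatic stoma have "increased direct costs related to stoma bags and associated products such as belts".

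**The concern.** A confounder must be able to affect, or share a cause with, both the choice of technique and the outcome. Exercise and garment use at 6 weeks, 6 months or 12 months come after the technique has been chosen and applied, so they cannot have influenced it.

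The question is then whether adjusting for them does harm. The protocol considers only whether technique changes behaviour directly. The study's premise, however, is that technique changes hernia risk, and a patient with a bulge or a leaking appliance may well start wearing a support garment or stop exercising. If so, technique does affect the behaviour, through the outcome, and blinding does not block that route.

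A model holding a 12-month garment record fixed would partly compare patients by whether they already had a hernia. The technique hazard ratios of objectives 3 to 6 are among the study's main results.

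**Working it through.** **1. Can the record follow the hernia?** Take a 12-month questionnaire that reports symptoms. A scan up to 6 months earlier counts, so the hernia may be confirmed by a scan at month 12 − 6 = 6. The 12-month garment record then comes up to 6 months after the event it would adjust for. For the 6-month questionnaire the window reaches back to month 6 − 6 = 0, so a 6-month record can also follow the scan. With roughly one usual-care scan a year, a hernia may also exist for months before the scan that dates it.

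**2. Does the document support an effect of hernia on behaviour?** Section 2.2.2 links symptomatic stomata to greater spending on products that include belts. This makes the path plausible; it does not measure it.

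**3. Size when garment use responds only to the CT-dated hernia.** The protocol gives no figures for garment use, so every behavioural input here is assumed. The proportional-hazards simulation used 60,000 patients, 4 repeats, 24 months, 35% two-year incidence (midway between the protocol's 30% and 40%), 30% garment use without a hernia, and garment odds multiplied by 3 or 6 once a hernia is present by 12 months. Baseline odds are 0.3/0.7 = 0.429. Three times that is 1.286 (56% use) and six times is 2.571 (72% use). Technique was unrelated to stoma type, and stoma type (hazard ratio 2) was in both models.

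| True technique HR | Garment odds × | HR without garment | HR with 12-month garment |
|---|---|---|---|
| 1.00 | 3 | 0.995 | 0.994 |
| 1.00 | 6 | 0.992 | 0.993 |
| 0.70 | 3 | 0.701 | 0.704 |
| 0.70 | 6 | 0.708 | 0.711 |
| 0.50 | 3 | 0.505 | 0.508 |
| 0.50 | 6 | 0.498 | 0.505 |

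A null effect does not move. A real effect moves towards 1 by 0.003 to 0.007. A second simulation, with a true hazard ratio of 1.5 and garment use rising from 30% to 60% (odds ratio 1.5/0.429 = 3.5), gave 1.51 without and 1.50 with the garment term.

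**4. Size when the hernia precedes its CT confirmation.** If the hernia changes behaviour before a scan dates it, adjustment removes more of the effect. The largest shift found was about 0.07 towards 1, for example 1.49 to 1.42. It depends on the delay to CT and on how strongly a hernia drives garment use, neither of which the protocol gives.

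**5. What 0.07 means against Table 3.** With exposure ratio 1:10, 40% incidence and squared correlation 0.5, Table 3 gives a detectable hazard ratio of 1.49 at 90% power and 1.41 at 80%. Events are 4000 × 0.4 = 1600. Information is 1600 × (1 − 0.5) × (1/11) × (10/11) = 66.1, with square root 8.13. For 1.49: ln(1.49) × 8.13 − 1.96 = 1.28, power 90%, which reproduces the table. For 1.42: ln(1.42) × 8.13 − 1.96 = 0.89, power about 81%. At this upper end, and with an unchanged standard error, the attenuation would cost about 9 points of power in that cell.

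**6. Table 5 beside the other sections.** Section 8.1 promises procedure and surgeon factors, and Table 5 lists none. Section 2.1 says reported hernia rates differ, "varying according to follow-up duration, stoma type and diagnosis method", and section 2.3 names open or laparoscopic approach as a possible factor; Table 5 has neither. Section 8.4 adjusts for approach in the economic comparison of mesh types. Sex appears only through parity, although section 13.2.1 collects gender.

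**The case against.** The strongest reply is that Table 5 is a list to be considered, not a fixed adjustment set. Section 8.1 leaves the model to the SAP, and section 4.8 keeps an instrumental-variable analysis open. The protocol fixes only when the behaviours are collected, so the SAP could use the 6-week value alone or model them as time-updated. This stands: actual mis-adjustment cannot be inferred from the protocol. It does not rescue the justification, which the protocol states outright and which overlooks the path through the hernia.

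A second reply is that the demonstrated effect is small. That also stands. A larger shift, from 1.50 to 1.62, appears only if garment use differs by 10 percentage points between techniques for reasons other than the hernia, which the protocol does not expect.

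On the omissions, the reply is that Table 5 mainly covers patient characteristics, while section 8.1 already commits to procedure and surgeon factors and to nesting within surgeon and centre. Stoma type is itself an exposure in objective 2. That is largely right, and leaves only a consistency edit.

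**Conclusion.** The point holds in a limited form. Two post-operative behaviours are labelled confounders, and the reason given leaves open the route by which they can become consequences of the outcome. If they entered as fixed covariates, hazard ratios for techniques that truly matter would be pulled towards 1, by between almost nothing and about 0.07. Under reverse causation alone a null effect did not move. These sizes rest on assumed garment use and an assumed delay to CT. They do not cover a behaviour that also shares unmeasured causes with hernia, which could be worse.

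A reader might infer two stronger things. One is that the technique hazard ratios are mis-adjusted; that is not shown, because the model is deferred.

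The other is that omitting stoma type builds in a large bias. Assume a 60/40 colostomy to ileostomy split, mesh in 15% and 3%, hernia in 40% and 20%, and inert mesh. Hernia risk is then 0.3765 with mesh and 0.3136 without, and ln(0.6235)/ln(0.6864) = 1.26. None of those inputs is in the protocol, no passage says stoma type drives technique, and indication for surgery, which is in Table 5, may absorb part of the effect. The figure is not an estimate of bias in the planned analysis.

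**What to change.** - Remove the Lifestyle and Behaviour group from the main adjustment list in Table 5. The items can still be collected and described.
- Replace the justification below the table with a statement that these behaviours follow surgery and may respond to a developing hernia.
- If adjustment for them is wanted, confine it to a sensitivity analysis using the 6-week value, and only where it was recorded before any hernia. The condition is needed because the CT window of the 6-month questionnaire reaches back to surgery.
- For consistency with sections 8.1, 2.1, 2.3 and 8.4, name stoma type, sex and open or laparoscopic approach as candidate confounders. State the role of approach for each comparison, since it may lie on the pathway for some techniques. Surgeon grade or specialty should not be added on this ground, because Phase B does not list it as collected.

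The cost is an edit to one table and its note. No new data should be needed: stoma type is required for objective 2, gender is collected, and approach is already an adjustment variable in section 8.4. Making the edit before accruing data are inspected under section 5.7 also guards against choosing covariates after seeing them.

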#### 5.8 Discontinuation/withdrawal of participants from the prospective cohort study

Each participant has the right to withdraw from the study at any time. If the participant wishes to withdraw, data collected until the time of the withdrawal will be included in the analysis unless the patient specifically requests for their data to be destroyed.

#### 5.9 Frequency and duration of follow up

Patients who consent to the prospective cohort study will be followed-up for a minimum of 2 years after their index procedure. Intervals of follow-up are specified in **Table 4**. Follow-up questionnaires will be issued by the coordinating centre (CTEU Bristol).

#### 5.10 Likely rate of loss to follow-up

In accordance with **Figure 1**, we expect that ≥90% of patients will complete follow-up or die within the minimum 2 year follow-up period, i.e. loss to follow-up of <10% for the primary outcome for reasons other than death. We will make all reasonable efforts to stay in contact with patients through the use of postal communication, email, text message and telephone. We will also use multiple sources to track participants during follow-up (see 5.4). About a further 15% are expected to die within two years; the reduced follow-up for these participants may impact on the power of the study to detect associations between PSH and surgical variants, depending on whether death occurs before or after ascertainment of a PSH. The impact of attrition due to death on the power of the study will be reviewed as data accrue to ensure that the study can address the objectives satisfactorily.

#### 5.11 Expenses

CIPHER is an observational cohort study that involves no deviation from the standard patient care pathway. Furthermore, there is no 'intervention' and therefore no costs will be accrued by patients. Accordingly, patients will not receive any funds / expenses for taking part.

#### 6. The Surgical Trainee Collaboratives (STCs)

The surgical trainee collaboratives (STCs) are organisations run by trainees and medical students that assist with multicentre clinical surgical research. The research team will engage with the STCs to promote the success and deliverability of CIPHER. We will develop a web application for trainees to use to grade CT scans (see 5.5). We anticipate engaging the STCs in three main capacities:

- Validating the ability of volunteer surgical trainees to grade PSH from CT scans; this will demonstrate that STCs can be trained to read CT scans, classify scans reproducibly and validly with respect to PSH according to the EHS classification and collect additional anatomical data from the scans (see 7).
- 2) Reviewing CT scans of participants in the CIPHER cohort. Scans will be reviewed and assessed (by STCs) according to the EHS classification system (see 4.6.1)
- 3) Involvement in the recruitment of patients and collection of essential study data with particular reference to data related to intraoperative manoeuvres (see 4.5).

#### 7. Training infrastructure for STCs

It will be necessary to train surgical trainees to assess the CT scans. Therefore, this protocol also describes the infrastructure we propose to establish to do this, since infrastructure does not exist outside the study and is required for it.

A selection of identifiable CT scans from patients with stomata have been obtained with consent by the Chief Investigator for a previous study and researchers carrying out Phase A of the CIPHER study. We will write to patients who gave permission for their CT scans to be

used previously and ask their consent to use their scans in the CIPHER study to train volunteer trainees to grade CT scans. All scans for which patients give their consent will be submitted to the CIPHER 'node' hosted by Sectra Ltd.

Trainees will be directed to view a training video to learn about the feature they are required to grade and how to use the CIPHER web application to record their assessments. The training CT scans will be able to be viewed through the IEP, just like CT scans obtained for participants in the main cohort. A range of training scans will be queued for assessment by a trainee. When the trainee is confident about carrying out the grading, he/she will be able to request the CTEU to queue a set of training CT scans. In order to be accepted as a grader for the main cohort study, a trainee will have to achieve 90% accuracy in assigning EHS PSH class, compared to the class assigned by an expert grader.

This group of patients will be similar to those recruited to the prospective cohort (having undergone stomata formation at our Cl's institution) and will be approach for their consent to use their images for the purposes of STC training and assessment. A patient information leaflet will explain the study and will be sent to patients along with a postal consent form. However, a PIL and consent form will only be sent to patients, once we have confirmed their survival status on NHS Spine. This is essential because the majority of this cohort have undergone bowel resection for cancer.

